# 2. LAY SUMMARY

Atrial fibrillation (AF) is the most common abnormal heart rhythm disturbance, affecting 1-2 million people in the UK. The irregular heartbeat caused by AF can make the heart pump blood less efficiently. This may lead to small blood clots forming inside the heart that, if they were to breakaway, can lead to blockage of small blood vessels. As a result, AF significantly increases the risk of having a stroke, heart failure and dementia. Despite having AF, a significant proportion of people have no symptoms, and they may be only found to be in AF after having a stroke. Therefore, diagnosis largely relies on accurate ECG monitoring.

AF episodes can be unpredictable, of very short duration and easily missed unless continuous ECG monitoring is undertaken. Pacemakers can continuously record the heart's electrical activity and detect AF with a high degree of confidence. However, they are invasive and rely on electrical wires implanted inside the heart, and hence less suited to be used as primary monitoring devices. To overcome these difficulties, implantable cardiac monitors (ICM) have been designed to be placed under the skin.

The new generation of ICMs has been miniaturised and are can now be injected under the skin. Moreover, they connect with the patient's smartphone and which can used to annotate symptoms and send ECG recording to their doctor when experiencing symptoms. Previous generation of ICMs could only transmit once a day (at night) and require close proximity to a home-based stationary monitor. This resulted in frequent failed transmission and delays from arrhythmic episodes detected by ICM and transmission to their physician.

Despite these significant improvements, their ability to reliably capture AF has never been tested against pacemakers.

The aim of this project is to study the performance of the two commonly used ICMs in detecting AF episodes and explore how the new connectivity can empower patients and improve patient care. We plan to inject an ICM in 30 patients with AF and pre-existing pacemaker. After a period of 6 months, we will compare how many episodes were detected in each device. With the information collected we will try to understand the pitfalls in the current technology and develop strategies to improve it.

Accurate, minimally-invasive long-term ECG monitoring can have far reaching benefits for patients, both in routine clinical practice and research. It can help identify AF in patients that have had an unexplained stroke, it can aid doctors' decisions in patients with infrequent but severe symptoms and monitor response to treatment. Furthermore, it is an important research tool that may provide more insight into the natural history of the disease and reliably test the efficacy of new drugs and procedures.

I

# 3. SYNOPSIS

Trial Title	Comparison of the performance of Implantable Cardiac Monitors and Cardiac Implantable Electronic Devices in detecting Atrial Fibrillation				
Internal ref. no. (or short title)	ID-AF				
Trial registration	Intended register – Clinicalt	rials.gov			
Sponsor	Oxford University Hospitals	NHS Foundation Trust			
Funder	Cardiac Rhythm Research H Abbott Medical Medtronic	ub (Oxford University Hospital	s)		
Clinical Phase	Pilot study				
Trial Design	Prospective, single centre, r	andomised observational stud	ly.		
Trial Participants		ith a dual-chamber CIED with or Persistent Atrial Fibrillation	a functioning		
Sample Size	30 subjects (15 on each investigation arm)				
Planned Trial Period	15 months Extension of study end date until 30 th June 2024				
Planned Recruitment period	<del>3 – 6 months</del> Extension of recruitment period until 31 st December 2023				
	Objectives	Outcome Measures	Timepoint(s)		
Primary	Primary Objective 1. To compare the performance of the Confirm Rx ™ ICM and Reveal LINQ ™ ICM in detecting clinically significant AF episodes (episodes longer than 6 minutes) to CIED (gold standard).	1. Confirm Rx and Reveal LINQ ™ ICM sensitivity, specificity, positive predictive value and negative predictive value will be calculated for AF episodes longer than 6 minutes	During follow-up (6 months)		
Secondary	Secondary Objectives				
	1. To compare the changes in R-wave amplitude following implantation in both ICMs.	
 
Compared the percentage of changes in R-wave amplitude between both ICMs
 
	1. During the follow- up period (6 month)		
	2. To compare the transmission success rate	
 
The percentage of successful transmission in both ICMs will be calculated.
 
	2. During the follow- up period (6 month)		

	of both devices. 3. To compare between both devices the number of patient- activated recordings that contains symptoms attributed to those episodes.	3. The percentage of activated recordings with symptoms will be calculated.	3. During follow-up period (6 months)
Intervention(s) 
 
Medical Device
 
	Implantable cardiac monito LINQ™(Medtronic)	ors (ICM): Confirm Rx™ (Abbo	tt) and Reveal
Comparator		ectronic Devices (Pacemak Implantable cardioverter-defi	

|

# 4. ABBREVIATIONS

٨٢	Adverse event
AE	Adverse event
AF	Atrial fibrillation
AR	Adverse Reaction
AT	Atrial Tachycardia
CI	Chief Investigator
CIED	Cardiac Implantable Electronic Device
CRF	Case Report Form
CRT	Cardiac Resynchronisation therapy
СТ	Clinical Trials
СТА	Clinical Trials Authorisation
CTRG	Clinical Trials and Research Governance
GCP	Good Clinical Practice
GP	General Practitioner
HRA	Health Research Authority
IB	Investigators Brochure
ICD	Implanted Cardioverter-Defibrillator
ICM	Implanted Cardiac Monitor
ICF	Informed Consent Form
IRB	Independent Review Board
NHS	National Health Service
RES	Research Ethics Service
PI	Principal Investigator
PIL	Participant/ Patient Information Leaflet
R&D	NHS Trust R&D Department
REC	Research Ethics Committee
RSI	Reference Safety Information
SAE	Serious Adverse Event
SOP	Standard Operating Procedure
TMF	Trial Master File

# 5. BACKGROUND AND RATIONALE

Clinical significance: Atrial fibrillation (AF) is the most common sustained arrhythmia affecting millions of people worldwide, leading to significant morbidity and mortality.  It is associated with a 5-fold increase risk of ischaemic stroke, accounting for 20-25% of all strokes which are generally more severe and disabling than non-AF related strokes. In addition, patients with AF have a 3-fold increase in heart failure and 2- fold increase in dementia.

Although the exact duration of AF required to cause a thromboembolic stroke is not known, episodes longer than 6 minutes detected by a CIED have been shown to increase the risk of stroke. Significant morbidity is associated with the duration and total burden of AF. Nonetheless, a large proportion of patients remains asymptomatic despite being in AF. In pacemaker patients, only 21% reported symptoms during AF episodes that were recorded by their device. In addition, the perception of AF related symptoms may change following an AF ablation with a 2-5 fold increase in the number of asymptomatic AF episodes. Thus, symptoms alone are unreliable in identifying the presence or absence of AF. Consequently, ECG monitoring tools play a critical role in the documentation of AF.

ECG monitoring: There is a correlation between the duration and intensity of ECG monitoring and the detection of AF, with continuous long-term ECG monitoring being superior to intermittent monitoring Continuous long-term ECG monitoring can be performed either intracardiac, with cardiac implantable electronic devices (CIED), or subcutaneously, with implantable cardiac monitors (ICM).

Dual-chamber cardiac implantable electronic devices (CIED): Pacemakers, ICDs, CRTs have excellent AF diagnostic capability with high sensitivity and specificity. The atrial lead is in direct contact with the atrial myocardium and generates high quality intracardiac electrograms (EGM) that are interpreted by advanced AF algorithms. However, the invasive nature of the procedure, potentially serious long-term complications, and high cost make them an inadequate primary arrhythmia monitoring device. Yet, in patients with pre-existing CIEDs, they can be used as a 'gold-standard' AF detection monitor to validate other devices.

First generation implantable cardiac monitors (ICM) were implanted subcutaneously, using blunt dissection, in the catherisation laboratory. Their AF detection algorithm was rudimentary, relying solely on irregular R-R intervals measurements. As a result, they were prone to false positive results caused by artefact and other irregular rhythms such as ventricular ectopy. The SMJ Confirm™ ICM had a sensitivity of 94% but a positive predictive value of only 64% for detection of clinically significant AF episodes (longer than 6 minutes). Furthermore, all ICMs transmissions to the Clinician's Web Portal required the subject to be within 2 metres of the home transmitter which resulted in suboptimal transmission success.

New generation Implantable cardiac monitors (ICM): They offer a minimally invasive approach for continuous ECG monitoring. ICMs outperform the external ambulatory ECG in the diagnosis of clinically significant arrhythmias in patients presenting with palpitations, syncope, cryptogenic stroke and post-AF ablation. . AF detection relies on a two-step approach. Firstly, they identify irregular R-R intervals and either a Markov chain model or Lorenzo plot to assign an AF probability score. Secondly, they review

the electrograms for any evidence of P waves. If no P waves are detected it is logged as AF. The two ICM to be studied are:

Reveal LINQTM ICM (MedtronicTM): Commonly used ICM with reported high sensitivity and positive predicted value. However, its AF algorithm has never been validated against CIED. Transmissions are performed through a home-monitor, 20% of which are unsuccessful I[4]. The most current version can use a smartphone app (MedtronicTM) and Bluetooth® connection to transmit the recording, however the transmission success rate has not been studied.

Confirm RxTM ICM X (AbbottTM): Was the first ICM equipped with Bluetooth® wireless technology that connects directly with the patient's smartphone via the myMerlinTM app (AbbottTM). The myMerlinTM app features include activation of ECG recordings when experiencing symptoms, viewing of transmission history to confirm successful data transfer and receiving notifications for scheduled transmission and device checks. Neither the AF algorithm nor the myMerlin App have been independently validated.

Only CE-marked devices and respective smartphone apps will be used in this trial .

## Future direction:

Injectable technologies have a large potential to improve the management of patients with AF, both as a diagnostic tool but also to guide therapies. However, its utility is dependent on having very sensitive, reasonably specific detection of clinically relevant AF episodes and high transmission success. This pilot study will investigate the accuracy of the new generation ICM and lay the foundation for future trials using different management strategies will be guided by ICM recordings and alerts from smartphone apps.

# 5. 1 Hypothesis

Injectable and wearable technologies have huge potential to improve the management of patients with AF, both as a diagnostic tool but also to guide therapies. "As-needed" use of oral anticoagulants has been proposed as a cost-effective way to prevent thromboembolic stroke as well as increasing patient compliance and satisfaction. However, its utility is dependent on having very sensitive, reasonably specific detection of clinically relevant AF episodes and high transmission success. It is therefore important to determine how accurate the latest devices and their detection algorithms are when compared to the gold standard of CIEDs (pacemakers, implantable cardiac defibrillators (ICD) and cardiac resynchronisation therapy (CRT) devices) that have atrial leads and constant monitoring

We hypothesize that the new generation ICMs (Confirm Rx™ and Reveal LINQ™) can identify the majority (sensitivity above 95%, positive predictive value above 85%) of clinically significant AF episodes (longer than 6 minutes). We also estimate that with Bluetooth® technology connecting to patients' smartphone will improve the transmission success rate above 80%.

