# 6. OBJECTIVES AND OUTCOME MEASURES

Objectives	Outcome Measures	Timepoint(s) of evaluation of this outcome measure (if applicable)
Primary Objective 1. To compare the performance of the Confirm Rx ™ ICM and Reveal LINQ ™ ICM in detecting clinically significant AF episodes (episodes longer than 6 minutes) to cardiac implantable electronic devices (CIED).	1. Confirm Rx and Reveal LINQ ™ ICM sensitivity, specificity, positive predictive value and negative predictive value will be calculated for AF episodes longer than 6 minutes	During follow-up (6 months)
Secondary Objectives		
1. To compare changes in the recording of electrograms (heart's electrical activity) R- wave amplitude from time of implant to end of follow-up (6 months)	
 
Compared the percentage of changes in R-wave amplitude between both ICMs
 
	1. During the follow- up period (6 month)
2. To compare the transmission success rate of episodes recorded by the implantable cardiac monitors to the Clinician's Web Portal.	2. The percentage of successful transmission in both ICMs will be calculated.	2. During the follow- up period (6 month)
3. To compare between both devices the number of patient-activated recordings that contains symptoms \\cts attributed to those episodes	3. The percentage of activated recordings with symptoms will be calculated.	3. During follow-up period (6 months)
Exploratory Objectives		
1. To study the changes in P-wave amplitude between different positions in the chest.	1. Percentage of change in P and R- wave amplitudes between V1 and V2 position. Percentage of change in P and R-wave amplitudes between surface	1. During implant

Trial Protocol	Version 1. 2 4 /Date: 0326/087/20234
ID-AF Study	IRAS Project number: 268739
Chief Investigator: [name]	- REC Ref: 21/LO/0508 ←
	Page 12 of 28

| |

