# 7. STUDY DESIGN

The ID-AF study is a prospective, single centre, randomised observational study aimed at comparing the performance of the Confirm  $Rx^{M}$  and Reveal LINQM ICMs in the detection of clinically relevant atrial fibrillation (AF) episodes to cardiac implantable electronic devices (CIED)

Subjects with pre-existing cardiac implanted electronic devices (Pacemakers, CRT and ICD devices) who have remote monitoring ability and are able to record electrograms will be identified by interrogation of the John Radcliffe Hospital Pacemaker Database. Subjects with a functioning atrial lead, on remote monitoring, non-permanent AF with an AF burden of more >2% in the last year will be invited to participate. Those who have expressed an interest in participating will be invited for an initial interview (eligibility assessment, baseline assessment and informed consent).

[figure not shown]
This study will randomise 30 subjects to receive either a Confirm Rx™ ICM or a Reveal LINQ™ ICM. The ICM will be implanted in the Outpatient setting as a Day Case Procedure according to manufacturer instructions. Prior to the implant, 2 minutes of recording in V1 and V2 position with the surface ICM mapping will be performed. The R-wave amplitude will be recorded at the end of the procedure. Subjects will be taught how to use the home-based transmitter and mobile app.

As it is standard of care, the research team will book a telephone follow-up appointment at 4-6 weeks to address any questions the subjects may have regarding the ICM, review ICM battery and wound. The ICMs are programmed for automatic daily transmissions of the recorded episodes to the Clinician's Web Portal. Scheduled remote transmissions for CIED will be performed at least monthly. At 6 months, subjects will be invited to attend a Device Clinic appointment for the final download from both devices. At this time, they may choose to have the ICM removed or left in-situ but turned off. During this last visit, ICM transmissions log will be interrogated. The end of the study for each patient will be the date of the 6 months follow-up appointment.

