# **11 STATISTICS AND ANALYSIS**

## 11.1 Sample size calculation

The largest study to date using ICMs was performed in 1049 patients with known AF which were followed for 3 months. AF episodes longer than 6 minutes were seen in 53% of patients who had, on average, 7 AF episodes per month. We will recruit patients with known high frequency of AF episodes therefore we can assume AF episodes in least 40% of patients during the 6 months study period. Using the Buderer's formula, 327 episodes of AF are required if the expected AF detection algorithm sensitivity is 95% and the specificity is 85% with a 95% confidence interval. Therefore, with a rate of 7 episodes per month a minimum of 8 subjects for each ICM is needed. We will aim to recruit 30 patients so that a broad spectrum of patient characteristics can be accounted for.

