## 11.2 Analysis of Outcome measures

Descriptive statistics are reported as count and percentage for categorical variables and mean and standard deviation for continuous variables.

The ICM performance will be investigated by calculating the sensitivity, specificity, positive predictive value and negative predictive value of AF episodes longer than 6 minutes will be calculated

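### Transmission success is to be compared with a historical 80%, but the plan reports only a percentage, with no interval and no allowance for repeated transmissions within a patient

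*Combined protocol and SAP*

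**What the plan says.** Section 5 (Background and Rationale) describes the Reveal LINQ as follows: "Transmissions are performed through a home-monitor, 20% of which are unsuccessful". Its newer version can transmit by smartphone app, "however the transmission success rate has not been studied". No success rate is given for the Confirm Rx by any route.

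Section 5.1 (Hypothesis) expects that Bluetooth connection to the patient's phone "will improve the transmission success rate above 80" per cent. No expected rate above 80% is stated.

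In section 6, secondary objective 2 is to compare the transmission success of the two monitors. The outcome measure is: "The percentage of successful transmission in both ICMs will be calculated". Section 11.2 adds only a general line, "Descriptive statistics are reported as count and percentage for categorical variables", and does not mention transmission. Section 11.1 sizes the study for AF detection alone.

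The Synopsis gives 15 subjects per arm. Section 7 sets the transmission pattern: "The ICMs are programmed for automatic daily transmissions of the recorded episodes to the Clinician's Web Portal". Follow-up is 6 months.

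**The concern.** The number that section 5.1 wants to exceed is the number that section 5 implies for the older route. A percentage calculated without any measure of uncertainty can only be set against 80% as a point estimate. A device that transmits no better than the old home monitor would then fall above or below 80% more or less by chance.

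The daily transmissions make this easy to overlook. Six months of them give each arm well over two thousand attempts, which looks like ample precision, but they come from only 15 patients. One patient with poor phone coverage or an unused app may fail for weeks. The precision of the rate therefore depends mainly on the number of patients, and nothing in the plan would show that.

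Sections 5 and 5.1 make high transmission success a condition for monitor-guided care, and section 5 presents this pilot as the foundation for later trials. An unsupported statement that smartphone transmission is better than the old system could be carried into their design.

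**Working it through.** **The plan's own sample-size figure.** Section 11.1 asks for 327 AF episodes and 8 subjects per device. With specificity 0.85, prevalence 0.40 and a half-width of 0.05 (not stated; assumed), Buderer's formula gives 1.96² × 0.85 × 0.15 / 0.05² / (1 − 0.40) = 326.5, rounded up to 327. Then 327 / (7 × 6) = 7.8, rounded up to 8. The figure reproduces, but it concerns AF detection and gives no basis for the transmission outcome.

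**Baseline.** 100% − 20% = 80%, the same value as the target.

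**Inputs for the check.**
- 15 patients per arm (Synopsis).
- Daily transmission for 6 months (section 7), taken as one attempt per day: about 182 per patient and 15 × 182 = 2,730 per arm. One attempt per day is an assumption.
- Within-patient correlation (ICC): not given. Assumed range 0.05 to 0.5.

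**Chance that the observed rate exceeds 80% when the true rate is 80%.**
- Independent transmissions, exact binomial: 48.4% with 630 transmissions, 49.2% with 2,730 (one arm), 49.5% with 5,460 (both arms pooled).
- Clustered by patient, beta-binomial simulation, 15 patients, ICC 0.05 to 0.5: 51.5 to 52.6%.
- Both devices must each exceed 80%: about 26 to 27%. At least one does: about 76 to 77%.

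The answer for one rate is about one half whatever correlation is assumed.

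**Effect of clustering on precision.** At a true 80%, the standard error of an arm's rate is √[0.80 × 0.20 × (ICC + (1 − ICC)/182) / 15].

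**Observed rate needed for the interval to lie above 80%.** Solve p − 2.145 × √[p(1 − p)(ICC + (1 − ICC)/182) / 15] = 0.80, where 2.145 is the two-sided 95% t value on 14 degrees of freedom.

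| ICC | Standard error at 80% | Observed rate needed | Interval above 80% when true rate is 80% | True rate 85% | True rate 90% |
|---|---|---|---|---|---|
| 0.1 | 3.3 points | 86% | 5% | 40% | 90% |
| 0.3 | 5.7 points | 89% | 7% | 25% | 59% |
| 0.5 | 7.3 points | 91% | 8% | 21% | 47% |

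The last three columns are simulated chances that the lower limit of a patient-level t interval exceeds 80%. At a true 80% they are above 2.5% because patient-level rates are skewed.

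**Sensitivity to the number of attempts.** Section 6 speaks of transmission of recorded episodes, so the denominator may be episodes and not days. With 7 × 6 = 42 attempts per patient in place of 182, the rates needed are 86.6%, 89.5% and 91.2%, so the number of attempts hardly matters.

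**The case against.** The strongest reply is that there is no decision rule to criticise. Section 5.1 hypothesises about AF detection but only estimates for transmission, and no section says that improvement will be concluded if the percentage exceeds 80%. This stands. A reader might infer that the protocol has adopted a test with a one-in-two false-positive rate, but it has adopted no test. The one-half figure describes what happens if the expectation in 5.1 is checked against the only output planned.

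A second reply is that 80% is the right reference: if the old system succeeds 80% of the time, improvement means exceeding 80%. This also stands. A reader might infer that the target itself is wrong, but the documents do not support that. The fault is that no uncertainty is attached to the estimate compared with it.

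Third, the stated objective compares the two devices with each other, and the 80% is a historical figure for one of them by one route. Its denominator and precision are not in the protocol. That limits how much weight any comparison with it can bear, and is a reason to label it. But section 5.1 speaks of improvement, so the comparison is already invited.

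Finally, the sensitivity target may look like the same fault: section 5.1 wants more than 95%, while section 11.1 says "the expected AF detection algorithm sensitivity is 95" per cent. The documents do not support extending the point to it. Section 11.1 is a precision calculation at an expected value, which is ordinary planning. Requiring a lower limit above 95% would turn the primary endpoint into a superiority test and would need its own sample-size case.

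**Conclusion.** The point holds for the transmission outcome. The plan names a historical value to beat but provides only a point estimate to set against it. For one device with a true rate still at 80%, that estimate would lie above 80% about half the time (49 to 53%). If both devices must pass, the figure is about a quarter.

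The one-half result does not depend on the assumed correlation or number of attempts. The 86 to 91% needed for a clear improvement rests on 15 analysable patients per arm, an assumed ICC of 0.1 to 0.5 and a t interval.

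Two limits remain after any change to the analysis. The 80% applies to the Reveal LINQ home monitor, with no counterpart for Confirm Rx. And section 8.9.1 allows the app or the home monitor depending on the device, whereas section 12.3 describes transmission by app. These sections need reconciling before the observed rate can be called a Bluetooth rate.

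This is a secondary outcome in a pilot. It should be corrected, but it does not threaten the primary analysis.

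**What to change.** In section 11.2, state that each monitor's transmission success will be reported with a two-sided 95% interval that takes the patient as the unit, from patient-level percentages or a bootstrap that resamples patients.

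In section 5.1, state that 80% is the historical Reveal LINQ home-monitor figure and that no equivalent is given for Confirm Rx. Add that a result will be described as an improvement on it only if the interval lies above 80%; otherwise the estimate and interval are reported without that claim.

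Leave the sensitivity target and its sample-size calculation out of this change.

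The cost is a few sentences, with no extra patients or data. The downside is that a real gain may be reported as not shown. With 15 patients per arm and a true rate of 90%, the interval would lie above 80% in about 90% of studies at an ICC of 0.1, but in only about 47% at 0.5.
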